5.4. Follow-up Period for Survival and Initiation of Anticancer Therapy

Post-treatment survival time and any subsequent anticancer therapy information status will be monitored approximately every 12 weeks (+/-3 weeks) from EOT Visit or more frequently as needed, until death, withdrawal of consent, or the study closes, whichever is earliest. This evaluation may be by record review and/or telephone contact.

6. DESCRIPTION OF STUDY TREATMENTS (ABI-009/NIVO)

6.1. ABI-009/Nivolumab Dosage, Administration, and Schedule

For the Phase 1 part of study, patients will receive nivolumab 3 mg/kg as IV infusion over 60 min every 3 weeks, followed by escalating doses of ABI-009 56, 75, 100 mg/m² for 2 of every 3 weeks by IV infusion over 30 minutes. ABI-009 will start on Day 8 of Cycle 2. If DLT develops in more than 1 patient at Dose 56 mg/m², the dose will be de-escalated to 45 mg/m² and to 30 mg/m² if DLT develops at 45 mg/m². Patients will continue therapy until unequivocal clinical disease progression, unacceptable toxicity, or until in the opinion of the investigator the patient is no longer benefiting from therapy, or at the patient's discretion.

For the Phase 2 part of study, patients will receive nivolumab 3 mg/kg as IV infusion over 30 min every 3 weeks, followed by ABI-009 at the MTD dose for 2 of every 3 weeks by IV infusion over 30 minutes. ABI-009 will start on Day 8 of Cycle 2. Patients will continue therapy until unequivocal clinical disease progression, unacceptable toxicity, or until in the opinion of the investigator the patient is no longer benefiting from therapy, or at the patient's discretion.

6.2. ABI-009 Dose Modification and Stopping Rules

6.2.1. Dosage Adjustments, Delays, Rules for Withholding or Restarting, Permanent Discontinuation

If, treatment cannot be administered on the planned visit date, ABI-009 may be administered +/- 2 days from the scheduled date. Prior to ABI-009 administration on Day 1 of each cycle, patients must meet the following hematological requirements:

- ANC $\geq 1.5 \times 10^9/L$
- Platelet count $\geq 100 \times 10^9/L$
- Hemoglobin $\geq 9 \text{ g/dL}$

The treatment will be on hold up to 14 days until the patient has fulfilled these criteria.

If a Grade 4 hematologic toxicity occurs, the dose of ABI-009 is held until toxicity resolves to Grade 1 or less. The dose of ABI-009 is then modified according to the dose modification section. If a Grade 3 non-hematologic toxicity occurs, both nivolumab and ABI-009 are withheld until toxicity resolves to Grade 1 or less. The dose of ABI-009 is then modified according to the dose modification section. Nivolumab has no dose modification.

The maximum delay between a missed scheduled dose and the next one (whichever dose was missed) should not be longer than 14 days. Approval from the Medical Monitor is required to restart study treatment after ≥ 21 days of interruption.

During the Phase 2 part of the study, doses of ABI-009 will be reduced for hematologic and other toxicities. Two levels of dose modifications are permitted according to the criteria below. If MTD is determined to be 56 mg/m², dose reductions will occur sequentially (45 mg/m² and 30 mg/m²), there should be no direct reduction by two dose

levels. If a toxicity requiring dose modification occurs following the second dose reduction of ABI-009, further treatment should be discontinued. Dose adjustments are to be made according to the system showing the greatest degree of toxicity. Toxicities will be graded using the NCI CTCAE Version 4.03.

Guidelines for dose modifications and interruptions for management of common toxicities associated with the study treatment(s) are provided in this section:

- General guidelines for clinically significant toxicities related to study treatment

And

- Specific guidelines for adverse events of special interest, which are events that have been observed with higher frequency or severity.

In the event of clinically significant AE in any part of the study, treatment may be withheld and supportive therapy administered as clinically indicated. If the toxicity or event is not grade 3/4 and resolves to baseline or grade 1 in less than or equal to 14 days of stopping therapy, then treatment may be restarted. Dose reduction of ABI-009 should be considered as clinically indicated.

If the toxicity does not resolve to at least grade 1 in less than 14 days, withdrawal from treatment with the IP is recommended. However, if the investigator and AADI Medical Monitor agree that further treatment would benefit the patient, treatment can continue with at least one dose level dose reduction, per Table 4.

Table 4. Dose Level Reduction Guidelines

Dose level	ABI-009 Dose/Schedule
1	Initial Dose: 56 mg/m ²
-1 (first dose reduction)	45 mg/m ²
-2 (second dose reduction)	30 mg/m ²

If an AE resolves to grade 1 or baseline at the reduced dose level, and no additional toxicities are seen during the following cycle of study treatment at the reduced dose, the dose may be increased to the previous dose level.

Any patient meeting the criteria for Hy's Law case (i.e. severe drug-induced liver injury) will be considered a dose-limiting toxicity. A Hy's Law case is defined as: AST or ALT values of $\geq 3 \times$ ULN AND with serum total bilirubin level (TBL) of $> 2 \times$ ULN without signs of cholestasis and with no other clear alternative reason to explain the observed liver-related laboratory abnormalities.

ABI-009 dose modification guidelines are outlined in Table 4 and Table 5

for clinically significant toxicities that are deemed related. The dosing schedule is described in the Schedule of Assessments, Table 2.

Table 5. Dose Modification Algorithms for Adverse Events Possibly Related to ABI-009

System/Organ	Adverse Event	CTCAE Grade v4.03	Dose modification Algorithm
Mucosa	Stomatitis, mucosal inflammation	Grade 2	Hold ABI-009 until resolution to Grade 1 or baseline and restart at the same dose for 1 st occurrence; for subsequent occurrences, drug will be restarted at a reduced dose; provide supportive care as clinically indicated.
		Grade ≥3	Hold ABI-009 until resolution to Grade 1 or baseline and restart at the same dose for 1 st occurrence for subsequent occurrences, drug will be restarted at a reduced dose; provide supportive care as clinically indicated.
Skin and Subcutaneous Tissue Disorders	Skin rash	Grade 2	Tolerable: Continue ABI 009 at full dose, monitor as clinically indicated
			Intolerable: Hold ABI-009 until resolution to Grade 1 or baseline and restart at the same dose for 1 st occurrence; for subsequent occurrences, drug will be restarted at a reduced dose; provide supportive care as clinically indicated.
		Grade ≥3	Hold ABI-009 until resolution to Grade 1 or baseline; for subsequent events, drug will be restarted at a reduced dose; provide supportive care as clinically indicated.
Gastrointestinal Disorders	Diarrhea despite optimal medication	Grade 2	Hold ABI-009 until resolution to Grade 1 or baseline and restart at the same dose for 1 st occurrences; for 2 nd and subsequent events, drug will be restarted at a reduced dose; provide supportive care as clinically indicated.
		Grade ≥3	Hold ABI-009 until resolution to Grade 1 or baseline; for subsequent events, drug will be restarted at a reduced dose; provide supportive care as clinically indicated.
Metabolic disorders	Hyperlipemia (cholesterol, triglycerides)	Grade 3	If this is persistent for 2 months, reduce by 1 dose level at start of next cycle

		Grade 4	If this is persistent for 1 month, reduce by 1 dose level at start of next cycle
	Hyperglycemia	Grades 1 and 2	Start at home 2x/day glucose monitoring; initiate medical management
		Grade 3	Initiate medical management ; If recurrent post ABI-009 despite adequate medical management, reduce by 1 dose level
		Grade 4	Initiate medical management, hold ABI-009 until grade 2 or less, restart 1 dose level lower
Hematologic toxicity	Thrombocytopenia, Neutropenia, Anemia	Grade 2	ABI-009 can resume once meeting the following hematological requirements: ANC > 1.5 x 10 ⁹ /L, platelets > 100 x 10 ⁹ /L and hemoglobin ≥9 g/dL
		Grade ≥3	Hold ABI-009 immediately for the remainder of that cycle. Repeat blood collection within 3 days. ABI-009 can resume once meeting following requirements: absolute ANC >1.5 x 10 ⁹ /L, platelet count > 100 x 10 ⁹ /L and hemoglobin ≥9 g/dL. For 2 nd and subsequent events, drug will be restarted at a reduced dose; G-CSF may be given as deemed indicated.
Respiratory events	Pneumonitis, bronchiolitis obliterans, and/or organizing pneumonia	Grade 2	Hold ABI-009 immediately for up to 3 weeks until resolved to ≤ grade 1, then reduce by 1 dose level. If it is still a Grade 2 after 3 weeks, discontinue treatment. If > Grade 2 recurs after resuming ABI-009 at a reduced dose level, discontinue treatment
		Grade ≥3	Permanently remove patient from protocol treatment

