Although rapamycin, an oral therapeutic, is an efficacious mTOR inhibitor, it has poor solubility, low oral bioavailability, and dose-limiting toxicity (29, 34). Marketed rapamycin analogs are temsirolimus and everolimus. Temsirolimus, approved for the treatment of kidney cancer, is a prodrug of rapamycin and requires conversion by the CYP3A enzyme. Everolimus is approved for pediatric and adult patients with subependymal giant cell astrocytoma, for advanced hormone receptor-positive, HER2-negative breast cancer in combination with exemestane, progressive neuroendocrine tumors of pancreatic origin (PNETs), subependymal giant cell astrocytoma (SEGA) associated with tuberous sclerosis and advanced renal cell carcinoma after failure of treatment with sunitinib or sorafenib (35-39).

Oral rapamycin and currently available rapalogs induce common side effects including hypertension, maculopapular rash (75%), mucositis (50%), asthenia (40%), nausea (43%), thrombocytopenia, metabolic abnormalities and more rarely pneumonitis (8%, 3% grade 3) sometimes fatal (40-42). The most frequently occurring grade 3 or 4 adverse events were hyperglycemia (17%), hypophosphatemia (13%), anemia (9%), and hypertriglyceridemia (6%) (43). These side effects could lead to the discontinuation of the treatment in 60% of patients in some studies.

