2.3. Study Design

This is an open label, dose-seeking phase 1/2 study using a defined dose of nivolumab and escalating doses of ABI-009 given intravenously.

I. Dose Escalation Phase 1 Part of Study: The study will employ the standard "cohort of three" design (Storer, 1989). Three patients are treated at each dose level with expansion to six patients per cohort if DLT is observed in one of the three initially-enrolled patients at each dose level. If no DLT occurs after 2 doses, escalation to the next dose level will be permitted. The maximum tolerated dose is defined as the highest safely tolerated dose, where not more than one patient experienced DLT, with the next higher dose level having at least two patients who experienced DLT. Patients in the dose escalation study may continue treatment at their designated dose levels up to eighteen 3-week treatment cycles or until significant disease progression or unacceptable toxicity occurs. No intra-patient dose escalation will take place.

Dose of nivolumab: 3 mg/kg IV over 30 min. q 3 weeks

NB: ABI-009 will start after 2nd Nivo dose, and will be administered on D8 and D15 beginning in C2.

Dose of ABI-009: Escalating doses IV over 30 min for 2 of every 3 weeks:

Treatment Cycle	# Pts.	Dose Level	Dose, mg/m2
Every 3 weeks	3-6	I	56
Every 3 weeks	3-6	II	75
Every 3 weeks	3-6	III	100

Note: DLT includes any \geq Grade 3 colitis, hepatitis, or pneumonitis, any Grade 1-2 colitis, hepatitis or pneumonitis that recurs, worsens or persists with oral steroids longer than 14 days, symptoms of adrenal crisis, any Grade 4 hematologic toxicity or any \geq Grade 3 non-hematologic toxicity.

II. Expansion Phase 2 Part of Study: Following dose escalation, an additional 22-28 patients will receive ABI-009 at the MTD and defined doses of nivolumab to assess overall safety and potential efficacy in a greater number of patients. Patients in the expansion

phase of the study may continue treatment up to 18 3-week treatment cycles or until significant disease progression or unacceptable toxicity occurs.

The study will be conducted in compliance with International Conference on Harmonisation (ICH) Good Clinical Practices (GCPs).

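### Section 6.2.1 withholds both drugs for a Grade 3 non-hematologic toxicity, but its Table 5 states no hold for Grade 3 hyperlipemia or hyperglycemia, and no precedence is written

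*Combined protocol and SAP*

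**What the plan says.** **General rule (Section 6.2.1).** "If a Grade 3 non-hematologic toxicity occurs, both nivolumab and ABI-009 are withheld until toxicity resolves to Grade 1 or less". The text goes on: "The dose of ABI-009 is then modified according to the dose modification section. Nivolumab has no dose modification". The gap between a missed dose and the next is limited to 14 days, and restarting after 21 days or more needs the Medical Monitor's approval. If a toxicity has not come down to Grade 1 in less than 14 days, withdrawal is recommended. The exception is that the investigator and the Medical Monitor may agree to continue with a reduction of at least one dose level.

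**Table 5 (same section; events possibly related to ABI-009).**
- Hyperlipemia, Grade 3: "If this is persistent for 2 months, reduce by 1 dose level at start of next cycle".
- Hyperlipemia, Grade 4: "If this is persistent for 1 month, reduce by 1 dose level at start of next cycle".
- Hyperglycemia, Grade 3: medical management, with a one-level reduction if it recurs despite that management. No hold is stated.
- Hyperglycemia, Grade 4: ABI-009 is held until Grade 2 or less, then restarted one level lower.
- Stomatitis or mucosal inflammation, Grade 3 or higher: "Hold ABI-009 until resolution to Grade 1 or baseline and restart at the same dose for 1" (first occurrence); the reduced dose applies from later occurrences.

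Section 6.2.1 announces both general guidelines and specific guidelines for events of special interest. It does not rank them.

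**DLT note (Synopsis and Section 2.3).** The list includes "symptoms of adrenal crisis, any Grade 4 hematologic toxicity or any \geq Grade 3 non-hematologic toxicity", with no exception for metabolic or laboratory events.

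**The concern.** For a Grade 3 rise in lipids or glucose, one part of Section 6.2.1 takes the patient off both drugs, while Table 5 states no hold. Both cannot be followed for the same patient. These are two stated rules that disagree, not a detail left open.

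At stake is consistent handling of patients within the trial. The planned summaries of exposure (Section 8.2) and of dose modifications and delays (Synopsis, safety assessments) would also mix patients managed under different rules.

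**Working it through.** **1. The rules side by side.**

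| Event | Section 6.2.1, general | Table 5 |
|---|---|---|
| Hyperlipemia, Grade 3 | Withhold both drugs to Grade 1 or less | No hold; reduce after 2 months' persistence |
| Hyperglycemia, Grade 3 | Withhold both drugs to Grade 1 or less | No hold; manage medically, reduce if recurrent |
| Stomatitis, Grade 3 or higher, first time | Withhold both drugs; ABI-009 dose then modified | Hold ABI-009; restart at same dose |

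The general sentence names Grade 3 only. The Grade 4 hyperlipemia row also states no hold, but applying the general rule to Grade 4 is an inference.

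**2. Is the missing hold deliberate?** For hyperglycemia, Table 5 does state a hold at Grade 4, so its absence at Grade 3 has meaning. For hyperlipemia, an instruction that waits for months of persistence presupposes that dosing goes on meanwhile.

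**3. Can the hyperlipemia row operate under the general rule?** Inputs are the 2-month and 1-month periods (Table 5), the 14-day limit (Section 6.2.1), and ABI-009 on Days 8 and 15 of a 21-day cycle (Section 2.3).
- Grade 3: 2 × 365.25/12 = 60.9 days; 60.9/14 = 4.3 times the limit.
- Grade 4: 365.25/12 = 30.4 days; 30.4/14 = 2.2 times the limit.
- A 61-day window is two full cycles (4 doses) plus 19 days (1 or 2 doses), so 5 or 6 scheduled doses. A 30-day window is one cycle (2 doses) plus 9 days (0 to 2 doses), so 2 to 4.

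Under the general hold, none of these doses is given while the event stays at Grade 3. The agreed exception to withdrawal does not rescue the row, because it brings in a dose reduction after about 14 days rather than 2 months. The hyperglycemia row is less absolute: it could still operate after a hold, but it does not ask for one.

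**4. Monitoring.** Fasting lipids are scheduled every 12 weeks (Section 5.2.1), which is 84 days. Scheduled tests alone cannot show persistence at 30 or 61 days; unscheduled tests would be needed.

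**5. Stomatitis.** The Grade 2 and Grade 3-or-higher texts are the same apart from one semicolon. Table 5 and the general rule agree that ABI-009 is held. They differ on the first restart: same dose in Table 5, modified dose in the general rule.

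**6. Escalation.** The cohort-of-three rule gives P(escalate) = (1−p)³ + 3p(1−p)⁵. At p = 0.10, 0.20, 0.30, 0.40 and 0.50 this is 0.906, 0.709, 0.494, 0.309 and 0.172, which reproduces the plan's Table 1 (0.91, 0.71, 0.49, 0.31, 0.17). The second term is the path on which one DLT occurs, the cohort expands to six, and the level still clears. At p = 0.20 the two terms are 0.512 + 0.197 = 0.709.

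**The case against.** The best reply is that the specific overrides the general. Section 6.2.1 announces two layers of guidance, Table 5 is naturally the specific layer, and the reference to the dose modification section can be read as pointing to it. On that reading the only defect is a missing sentence on precedence. The reading is reasonable, but it is not written down. The general rule has no exception, and it places the hold first with dose modification afterwards. The instruction to follow the system with the greatest toxicity ranks organ systems, not sections. Restricting Table 5 to events possibly related to ABI-009 does not help either, since such events are still Grade 3 non-hematologic toxicities.

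The reply carries more weight for stomatitis. Table 5 may itself be the modification that the general rule refers to, which is why that point is lesser. A reader might also infer that Table 5 lets nivolumab continue. It does not say so. It is an ABI-009 table, and its silence leaves the general hold on nivolumab in place.

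Three stronger readings about the maximum tolerated dose (MTD) are tempting but not supported:
- *The MTD depends on whether the general rule or Table 5 is followed.* The DLT note covers these events without exception, and neither management rule alters that. An event can count as a DLT while the patient stays on drug.
- *One such event stops escalation.* One DLT in three expands the cohort to six; the MTD definition needs at least two patients with DLT at the next higher level.
- *The effect can be sized from Section 1.2.1.* That section reports "The most frequently occurring grade 3 or 4 adverse events were hyperglycemia (17%), hypophosphatemia (13%), anemia (9%), and hypertriglyceridemia (6"%). Put into the formula above, 17% gives 0.77 and 17 + 13 + 6 = 36% gives 0.38. But hypophosphatemia has no Table 5 row, and the rates are for oral rapamycin and rapalogs, Grades 3 and 4 combined, with no link to the two-dose escalation window. If those two doses are of ABI-009, they fall on Days 29 and 36 (Cycle 2, Days 8 and 15), before a 12-week lipid test. Section 1.2.4's summary of the ABI-009 Phase 1 study does not mention hyperglycemia and gives hypertriglyceridemia as 15% over all grades.

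**Conclusion.** The conflict is real for Grade 3 hyperlipemia and Grade 3 hyperglycemia. The hyperlipemia row cannot work as written if the general rule is followed, because its waiting period is more than four times the permitted delay. The hyperglycemia row omits a hold that the general rule requires. The restart dose after a first Grade 3 or higher stomatitis is a smaller mismatch.

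The conclusion rests on the text and on two readings: that no stated hold means dosing continues (supported by the Grade 4 hyperglycemia row and the persistence periods), and that the general rule applies to metabolic events (it makes no exception). It needs no event rate, and no effect on the MTD is claimed. The DLT note is not in contradiction with Table 5. It does make dose-limiting some events that Table 5 manages without a hold, and the plan should say whether that is meant.

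**What to change.** Reconcile the general Grade 3 rule, the 14-day delay and withdrawal text, and Table 5, all in Section 6.2.1. State which governs for the events listed in Table 5, including the restart dose after a first Grade 3 or higher stomatitis. If persistence periods for hyperlipemia are kept, say how persistence is established given lipid tests every 12 weeks.

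In the same revision, confirm in the Synopsis and Section 2.3 whether Grade 3 metabolic laboratory events that Table 5 manages without a hold are meant to count as DLTs, as the current note makes them. The clinical choice is the sponsor's, and none is proposed here.

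The cost is wording in the Synopsis, Section 2.3, Section 6.2.1 and Table 5. Sample size and analysis methods are unchanged.

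### Section 6.2.1 and its own Table 5 give inconsistent hold, delay, restart and dose rules for Grade 3-4 hematologic toxicity, and nothing says which prevails

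*Combined protocol and SAP*

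**What the plan says.** Three parts of Section 6.2.1 bear on a Grade 3-4 blood-count event.

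- **Opening text.** It has an event rule for Grade 4: "If a Grade 4 hematologic toxicity occurs, the dose of ABI-009 is held until toxicity resolves to Grade 1 or less", followed by "The dose of ABI-009 is then modified according to the dose modification section". It has no event rule for Grade 3. It sets a 14-day maximum delay between a missed dose and the next one. It also has a pre-dose count check (ANC at least 1.5 and platelets at least 100, both × 10⁹/L; hemoglobin at least 9 g/dL), tied to ABI-009 given on Day 1 of a cycle.
- **General guidance before Table 4.** For any clinically significant event, "treatment may be withheld and supportive therapy administered as clinically indicated". Its restart sentence begins "If the toxicity or event is not grade 3/4 and resolves to baseline or grade 1 in less than or equal to 14 days". An event that has not returned to Grade 1 in under 14 days leads to recommended withdrawal. If the investigator and the medical monitor agree to go on, the dose falls by at least one level.
- **Table 5, hematologic row, Grade 3 or higher.** "Hold ABI-009 immediately for the remainder of that cycle". Then "ABI-009 can resume once meeting following requirements: absolute ANC >1.5 x 10" (× 10⁹/L), with platelets above 100 and hemoglobin at least 9 g/dL. No time limit is given. For second and "subsequent events, drug will be restarted at a reduced dose; G-CSF may be given as deemed indicated".

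No sentence says whether the table or the text governs when they differ.

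**The concern.** A site treating one patient can follow one part of Section 6.2.1 and depart from another. The differences affect whether a scheduled dose is given, how long the gap may be, whether the patient is withdrawn, and whether the dose must fall on restart.

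This is first a matter of patient safety, but it also reaches the data. Dose modifications, delays and discontinuations are listed among the key safety assessments in the synopsis, and Section 8.2 summarizes exposure. Section 2.3 permits escalation when no DLT has occurred after 2 doses. Section 8.3 admits to the Efficacy Analysis Dataset only patients with at least two doses of ABI-009. A hold or withdrawal after the first ABI-009 dose can therefore affect who contributes to each.

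**Working it through.** The plan states no figure on this point, so there is none to reproduce. The check sets the rules side by side and runs them on the dosing calendar.

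**Inputs.** ABI-009 on Days 8 and 15 of a 21-day cycle from Cycle 2 (Sections 1.4 and 2.3). Dosing window ±2 days, maximum delay 14 days, slow-recovery limit 14 days (all Section 6.2.1). Days are counted from Day 1 of the cycle in which the event is found. Day 8 of the next cycle is 21 + 8 = Day 29; Day 15 of the previous cycle is 15 − 21 = Day −6.

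**Case 1: Grade 4 found on Day 8, at Grade 1 and above the Table 5 counts by Day 15.** Under the opening text the hold is over and a Day 15 dose can be given. Under Table 5, Day 15 still lies in the held cycle and the next dose is Day 29. The rules differ by 1 of the cycle's 2 doses.

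**Case 2: Table 5 hold against the delay limit.**

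| Event found | Doses missed | First missed to next | Last missed to next | Last given to next |
|---|---|---|---|---|
| Day 8 | Days 8 and 15 | 29 − 8 = 21 days | 29 − 15 = 14 days | 29 − (−6) = 35 days |
| Day 15 | Day 15 | 29 − 15 = 14 days | 14 days | 29 − 8 = 21 days |

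For a Day 8 event, dosing two days early shortens 21 days to 19, still above 14. Counted from the second missed dose, the gap is exactly 14. Whether following Table 5 breaches the limit therefore depends on which missed dose starts the clock.

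**Case 3: Grade 3 found on Day 8.** Table 5 requires a hold. The opening text has no event rule, and the general guidance only permits one.

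**Case 4: first Grade 3-4 event that reaches Grade 1 and the counts only after 14 days.** The general guidance recommends withdrawal, or continuation at least one dose level lower. Table 5 allows resumption and calls for no reduction, because this is not a second event.

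**Case 5: recovery criteria.** The opening text uses a grade for the Grade 4 event; Table 5 uses counts. The printed counts also differ at the boundary: an ANC of exactly 1.5 or platelets of exactly 100 pass the pre-dose check but not Table 5. That check names Day 1, when no ABI-009 is scheduled, so as written it does not apply before a Day 8 or Day 15 dose.

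**Effect on the second ABI-009 dose.** Suppose the first dose is Cycle 2 Day 8 and a Grade 4 event appears and resolves before Day 15. The opening text lets the second dose fall on Day 15. Table 5 moves it to Cycle 3 Day 8, 29 − 15 = 14 days later. If recovery is slow, withdrawal means no second dose and no entry to the Efficacy Analysis Dataset. Under Table 5 the patient may resume and could still qualify.

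**The case against.** The best defence is that Section 6.2.1 announces general and specific guidelines, so Table 5 can be read as the specific tier that overrides the rest. That is a reasonable reading, but the section never states it, and the Grade 4 sentence in the opening text is itself specific to hematologic events. The delay limit is also softened: it is worded as something that should not be exceeded, and the next sentence provides for medical monitor approval after interruptions of 21 days or more. That makes the delay conflict less absolute without removing it.

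Several stronger readings might be inferred, and the documents do not support them:

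- *The text would have a Grade 3 patient dosed.* The opening text is silent on Grade 3; it does not order dosing. Setting Table 5 against it as all of a cycle's doses lost versus none compares a rule with silence.
- *After a first Grade 4 event the opening text demands a reduction and Table 5 demands the same dose.* The sentence "The dose of ABI-009 is then modified according to the dose modification section" reads naturally as a cross-reference to Tables 4 and 5. The hematologic row does not say same dose for a first event, although some other rows do. The conflict on dose rests on the 14-day slow-recovery rule.
- *The general guidance bars restart after Grade 3-4.* It permits restart for lesser events and leaves the rest unaddressed.
- *The recovery counts contradict Grade 1.* That needs grade cut-offs that the documents do not print.

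**Conclusion.** The inconsistency is real and the section is wrong as written. The firm parts are the end of the Grade 4 hold, which can differ by one dose in a cycle, and the handling of a slow-recovering first event. That event leads to withdrawal or a reduced dose under the general guidance, and to resumption with no required reduction under Table 5. The delay conflict is 21 days against 14, or none, depending on which missed dose starts the clock.

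How often this will arise cannot be estimated well. In the background study (Section 1.2.4) there was one Grade 4 hematologic event among 26 patients (1/26, about 4%), at 150 mg/m², above this trial's top level of 100 mg/m². At 100 mg/m² the only hematologic event was a Grade 3 anemia. That study gave ABI-009 on a different schedule and its description mentions no nivolumab, so it is limited evidence. The all-grade rates quoted there, mostly Grade 1-2, do not measure this problem.

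A reader might infer that the MTD is compromised because the DLT count depends on which rule is followed. It does not for the event itself: Grade 4 hematologic toxicity is a DLT when it occurs, and later handling does not undo it. The effect falls on patient safety, exposure, discontinuation counts and receipt of the second ABI-009 dose. The calendar results assume doses on the scheduled days except where the two-day window is shown. The link to escalation assumes that the 2 doses in Section 2.3 are ABI-009 doses.

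**What to change.** Reconcile the opening text, the general guidance and the Table 5 hematologic row of Section 6.2.1 into one consistent set of rules. It should cover:

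- what triggers a hold and what ends it;
- the recovery criterion, in one form and with one boundary convention;
- the maximum delay and the missed dose from which it is counted;
- what follows slow recovery;
- the dose on restart at first and later events;
- the day to which the pre-dose count check applies.

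Separate Grade 3 and Grade 4 provisions are acceptable. Alternatively, keep the passages and state which takes precedence. The clinical content is for the sponsor to set. The cost is amendment wording only; sample size and analysis methods do not change.
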